
Analysis & Interpretation. The primary outcome (death or NDI at 18-22 months corrected age) will be analyzed in standard logistic regression equations in which the predictor variables include center, and level of risk at enrollment as determined by the method described above. Separate analyses will be used to assess whether there is an interaction between treatment (laparotomy or drainage) and disease (NEC or IP). Secondary analyses of randomized patients will be performed using Bayesian methods to assess the (posterior) probability that laparotomy reduces death or NDI relative to that with drainage.

Consent to randomization may be unobtainable before surgery for a sizable proportion of infants. Providing parents at least agree to collection of the same baseline and outcome data as for randomized infants, we will relate surgical treatment to risk adjusted outcome. A finding that the risk adjusted relative risk in the nonrandomized patients is similar to the relative risk observed in the randomized patients will support the validity of the trial results and generalizability of the results among randomized patients to nonrandomized patients. (This would be expected based on a prior meta analysis of studies using a comprehensive cohort design [JAMA 2005]). Whether use of propensity scoring also supports the results among randomized patients will also be assessed.

Sample Size and Resources. Based on our observational study, we hypothesize that 80% of drain infants and 65% of the laparotomy infants will die or be impaired (NNT = only 7 to gain one unimpaired survivor); 300 infants (150 / group) whose primary outcome is determined will be needed (alpha =0.05 & beta = 0.20, two sided Fisher exact test). Enrollment will likely require 4 years (assuming a consent rate of 50%) unless the consent rate is higher than projected. We propose to initiate this trial within Network sites initially given the importance and urgency of the clinical question. Enrollment will be prospectively monitored and if found to be low after 6 months (after 80% of participating centers have IRB approval and are actively participating in the trial), consideration will be given to add additional sites. Despite the difficulties anticipated with the proposed trial, the total expense and effort required will be small relative to other Network trials, and the trial may facilitate future trials involving urgent/emergent therapies, rare diseases, or surgical interventions.

TRIAL OBJECTIVES

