We are proposing to conduct this trial purely within the Network as long as adequate enrollment can be achieved. If enrollment is below the predicted rate that would allow completion of the trial in 4 years, we would propose to add additional sites as needed to allow adequate enrollment. Both randomized trials published in this area have been halted prior to achieving the desired sample size. It would be unwise to ignore this history. Thus, we propose to critically evaluate actual versus desired enrollment at 6 months and carefully consider the need / desirability of recruiting additional sites.

Comprehensive cohort design. This design differs from that of a conventional randomized trial by including not only patients whose treatment is randomly assigned but also any whose treatment is based on the preference of the physician or patient (or surrogate). When properly performed, every effort is made in these trials to promote clinical equipoise and obtain informed consent to be randomized. If such consent is refused, consent is sought only for data collection. Whenever possible, the determination of primary outcome is carefully standardized and assessed by masked evaluators. Baseline data are carefully collected and controlled during analysis to adjust for baseline differences between patients who receive different therapies.

This approach has the potential advantage of increasing the number of patients studied and the external validity (generalizability) of the results by involving patients and physicians who otherwise would not be involved.¹⁰ However, an increase in external validity would be important only if the internal validity of the results is not undermined. Based on surveys of purely observational studies, one would expect that inclusion of preference groups would bias the results. This problem might be avoided or minimized because of measures to promote equipoise prior to the study, stringent features of study design and analysis as noted above,

exclusion of centers with such strong biases that they are unwilling to randomize any patients, and the balancing of biases within and between centers that do participate. A systematic review published in JAMA this year¹⁰ assessed all trials using a comprehensive cohort design. The review concluded that “Differences in outcome between randomized and preference groups were generally small, particularly in large trials and after accounting for baseline measures of risk”.

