the Bayley tests. We plan to critically examine these data (GDB data, pooled data from NEST study subjects, and publicized data from other studies) at yearly intervals during the trial enrollment period. The sample size determination will be reevaluated, and may be revised upwards as the uncertainty regarding the Bayley III lessens (2 years after study commencement). These decisions will be made by the Steering Committee based upon a recommendation by the NEST subcommittee, and without any knowledge of the difference between the two treatment groups in this trial with regard to the proportion of impaired children.

Sample Size. Allowing for a smaller difference between treatment groups in the trial than in our observational study, we hypothesize that 80% of the drain group and 65% of the laparotomy group will die or be impaired at 18-22 mo. (Number needed to treat = only 7 to gain one unimpaired survivor from laparotomy). By PASS software, a total sample size of 300 infants who have their outcome assessed is needed with $\alpha = 0.05$ and $\beta = 0.20$ using 2-sided Fisher exact test.

In the observational study 156 infants were enrolled in 14 centers in 18 months. By extrapolating these numbers to a 16-center trial design, 120 eligible patients / year would be expected. Based on the latest GDB data, using the 16 centers prior to reformatting the Network, an estimated number of eligible babies of 190 is obtained. Our best estimate of the number of eligible patients in the new 16-center Network is 160 / year. We anticipate a 50% enrollment rate, $\geq 95\%$ consent for data collection (as for generic data collection), equal use of initial laparotomy and drains; and a 50% mortality in each group. Assuming a consent rate of 50%, 320 patients would be enrolled in a 4-year period with 160 deaths and 160 survivors. With a 90% follow up rate, 144 survivors would have the primary outcome measured. This would yield 304 patients which will meet our sample size requirement during a 4-year enrollment period. If the consent rate is below 50%, the enrollment period would need to be extended.

We propose that the trial be stopped when any of the following are met: 1) DSMC might stop trial for large difference in neonatal mortality (secondary outcome), which is unlikely given equivalent survival in both observational study and two randomized trials; 2) 300 randomized patients are enrolled and have primary outcome assessed; or 3) a 5-year enrollment period has elapsed.

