To control the Type I error associated with sequential testing of the primary efficacy endpoint, O'Brien-Fleming boundaries will be calculated for three interim and one final analysis. Since we cannot precisely predict beforehand what proportion of trial enrollees will have primary outcome data available before each of these meetings, we will use the Lan DeMets approximation to the O'Brien-Fleming sequential monitoring bounds to account for unequally spaced interim analyses. Original power calculations based on Fisher's exact test indicated that 150 infants per arm would be sufficient for 80% power if 80% and 65% of infants experienced death or NDI in the Drain and Laparotomy arms respectively. Additional simulations were used to estimate power using the following interim analysis plan and a robust Poisson regression model to estimate treatment effect, under the above-mentioned trial assumptions. The estimated power was 82%.

Interim efficacy assessments will be completed at approximately 75, 150, and 225 randomized infants who are at least 22 months corrected age regardless of death. A final analysis will occur at 300 randomized infants and will account for the earlier looks. The following R code was used to predict the O'Brien-Fleming boundaries under these assumptions:

```
library(gsDesign)
OF.design <- gsDesign(k=4, test.type=2, n.I=c(75, 150, 225, 300),
                      sfu="OF")
OF.design$upper$bound
```

In this call to `gsDesign()`, "k" equals the total number of planned efficacy analyses (interim + final), "test.type" equals 2 so the design is two-sided with symmetrical boundaries, and "sfu" equals OF to indicate O'Brien-Fleming boundaries. Note that only an upper bound spending function was specified since the design is symmetrical. The above call to the `gsDesign` function resulted in the following boundaries:

Interim Analysis	Lower Boundary	Upper Boundary
1	-4.05	4.05
2	-2.86	2.86
3	-2.34	2.34
4	-2.02	2.02

Since this design is two-sided and not 'closed', it is possible that the study could end without one arm being identified as better than the other. As such, the potential 'beta'

error in this design is the failure to reject a false null hypothesis and not the failure to accept a false null hypothesis.

Because actual enrollment at the time of each interim efficacy analysis will not occur exactly as planned, boundaries will be recalculated using the following R code:

```
OF.update <- gsDesign(k=L, test.type=2, n.I=vec.L, sfu=sfLDOF,

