maxn.IPlan=300)
OF.update$upper$bound
```

where L equals the total number of completed and still to complete looks such as 4, and $vec.L$ contains a modified list of sample sizes at the exact and still to be completed looks such as $c(81,150,225,300)$. Note that the spending function is now “sfLDOF”, which specifies that the boundaries will be recalculated given new sample size points based on the Lan-DeMets approximation of O’Brien-Fleming boundaries.

At the time of each interim analysis, the boundaries for the current and future interim analyses will be updated using `gsDesign()` as described above. A robust Poisson regression model will be used to analyze the primary outcome of death or NDI at 18-22 months. For the robust Poisson regression, the outcome for the i^{th} infant will be:

$$y_i = \begin{cases} 0 & \text{for survival without NDI} \\ 1 & \text{for death or survival with NDI} \end{cases}$$

The covariates will have the form:

$$s_i = \begin{cases} 0 & \text{initial surgery was drain} \\ 1 & \text{initial surgery was laparotomy} \end{cases}$$

$$r_i = \begin{cases} 0 & \text{low baseline risk for death or NDI} \\ 1 & \text{high baseline risk for death or NDI} \end{cases}$$

The model will have the form:

$$y_i | (s_i, r_i, c_i) \sim \text{Poisson}[\lambda(s_i, r_i, c_i)], \text{ where } \log[\lambda] = \alpha + \vartheta \cdot s_i + \gamma \cdot r_i + \nu_c \cdot c_i \text{ and } c_i \text{ represents the site for the } i^{\text{th}} \text{ infant among } C \text{ total sites.}$$

Similar to the safety interim analysis, the test statistic produced for the treatment effect will be a z-statistic. This z-statistic will be compared to the appropriate boundary pair calculated from the updating call to `gsDesign()`. The actual robust regression modeling at each interim analysis will be completed in SAS, and a figure summarizing the interim

analysis results will be constructed in Excel. Prior interim analysis results will be represented in the figure as well.

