The primary analysis of randomized cohort data will assess the effect of treatment on death or NDI at 18-22 months corrected age, death, and other clinical outcomes as defined in Study Endpoint section above (pages 8-10) and listed on pages 13 and 14. This analysis will be performed using a robust Poisson regression model identical to the model defined on page 17 and 18. If possible center will also be included in the model as a fixed or random effect. The default will be a fixed effect, but a random effect may be used if model convergence issues results from using a fixed effect. The outcome variable will assign one to the event of death or NDI at 18-22 months corrected age and zero otherwise. The treatment variable will assign one to laparotomy and zero to drainage. It follows that relative risks less than one (or less than zero on the log scale) will favor Laparotomy.

Like the efficacy interim analysis, the final test statistic produced for the treatment effect will be a z-statistic. This z-statistic will be compared to the appropriate boundary pair calculated from the updating call to `gsDesign()` as described in the efficacy interim analysis section. As with the interim efficacy analyses, the actual robust regression modeling at each interim analysis will be completed in SAS, and a figure summarizing the final analysis results will be constructed in Excel. This figure will contain information from all prior interim efficacy analysis results.

In addition to the above formal adjusted analyses, simple unadjusted treatment comparisons of randomized data will be completed, and 95% confidence intervals of differences in proportions will be constructed. The formatting of these tabulations will be determined as the corresponding papers develop.

Secondary Analysis of Primary Outcome Using Randomized Cohort Data

The analyses will include an assessment of whether there is an interaction between treatment (laparotomy or drainage) and disease (NEC or IP). This assessment will use a robust Poisson regression model with will include treatment (laparotomy or drainage), preoperative diagnosis (NEC or IP), and the treatment by preoperative diagnosis interaction. If the Wald test for the interaction term has a p-value less than 0.05, then the conclusion will be the study has produced evidence of an interaction between treatment and pre-operative diagnosis with respect to the primary outcome. If such

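### The SAP's boundary update keeps a planned maximum of 300 even at the final analysis, so if enrollment ends short at five years, part of the 5% alpha may go unspent

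*SAP*

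**What the plan says.** The SAP section Interim Efficiency Assessment plans efficacy looks at about 75, 150 and 225 randomized infants who have reached 22 months corrected age, and a final analysis at 300 randomized infants. Because the looks will not fall exactly as planned, the boundaries are updated with a second `gsDesign` call. Its spending function, according to the SAP, "specifies that the boundaries will be recalculated given new sample size points based on the Lan-DeMets approximation" of the O'Brien-Fleming limits. The call takes a vector, `vec.L`, of the sample sizes already reached and those still planned, and separately fixes "maxn.IPlan=300". The one example vector ends at 300.

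The final test uses the same device. In Primary Analysis of Randomized Cohort Data the SAP says of the final statistic: "This z-statistic will be compared to the appropriate boundary pair calculated from the updating call to" `gsDesign()`.

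The protocol (Sample Size) lists three conditions, any of which ends the trial. One is reaching 300 randomized infants with the outcome assessed. Another is "3) a 5-year enrollment period has elapsed", with no minimum number attached. Under Critical Design Issues the protocol also warns: "Both randomized trials published in this area have been halted prior to achieving the desired sample size".

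Neither document says how the last boundary is derived if the final number is below 300.

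**The concern.** A Lan-DeMets function ties the alpha spent so far to the fraction of planned information reached. At interim looks a fixed denominator of 300 is right, because alpha has to be kept for later looks. At the last look there is nothing to keep it for. If the fraction is still taken as N/300 with N below 300, the rule reserves alpha for an analysis that will never take place, and the final critical value is higher than a 5% test needs.

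This is the critical value for the only hypothesis the trial was powered to test. The loss would also fall in the situation where power is already short, that is, when recruitment has run out of time.

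**Working it through.** **Inputs.** Two-sided 5% and 80% power ("alpha =0.05 & beta = 0.20, two sided Fisher exact test", protocol abstract). Event rates: "80% of the drain group and 65% of the laparotomy group will die or be impaired at 18-22 mo" (protocol, Sample Size), a relative risk of 0.65/0.80 = 0.8125. Size: "150 infants per arm would be sufficient for 80% power" (SAP, Interim Efficiency Assessment). Looks at 75, 150, 225 and a final N.

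**1. The plan's own figures reproduce.** Recursive numerical integration for classical O'Brien-Fleming limits with four equal looks and 0.025 per tail gives 4.049, 2.863, 2.337 and 2.024; the SAP prints 4.05, 2.86, 2.34 and 2.02. Exact Fisher power at 150 per arm is 80.3% (stated 80%). A simulated robust log relative risk test without covariates, using the printed boundaries, gives 82.3% (stated 82%).

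**2. The updated boundaries when the final look is at 300.** Lan-DeMets O'Brien-Fleming spending per tail is

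α(t) = 2 − 2Φ(z / √t), with z = Φ⁻¹(1 − 0.0125) = 2.241 and t = n/300.

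At t = 0.25, 0.50, 0.75 and 1 this gives 0.000007, 0.0015, 0.0096 and 0.0250. The boundaries are 4.333, 2.963, 2.359 and 2.014. At 300 the rule spends the full 5%.

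**3. A final look below 300.** Take N = 270, so t = 0.90. Then 2.241/√0.90 = 2.363 and α = 2 × 0.00907 = 0.0181 per tail, or 3.6% two-sided. The remaining 1.4 percentage points are never used.

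**4. Size.** The drift at 300 is |log 0.8125| / √[(0.35/0.65 + 0.20/0.80)/150] = 0.2076/0.0725 = 2.86. At look size n the expected z is 2.86 × √(n/300). In each pair, the first figure spends at N/300 at the last look and the second spends all remaining alpha there.

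| Final N | Final critical value | Two-sided alpha | Power |
|---|---|---|---|
| 300 | 2.014 / 2.014 | 5.0% / 5.0% | 81.0% / 81.0% |
| 297 | 2.028 / 2.012 | 4.9% / 5.0% | 80.2% / 80.6% |
| 270 | 2.165 / 1.993 | 3.6% / 5.0% | 72.3% / 77.1% |
| 240 | 2.348 / 1.969 | 2.4% / 5.0% | 61.1% / 72.5% |

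**5. Checks.** Simulating binary outcomes with these boundaries gives the same picture. At 270, power is 73.4% against 78.4% and type I error 3.4% against 4.8%. At 240, power is 62.2% against 74.2% and type I error 2.3% against 5.0%. The alpha left unspent depends only on the last N, not on the number of looks: with looks at 75, 150 and 270 it is again 3.6% spent, with a final value of 2.105 instead of 1.967.

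**6. Can the final number fall below 300?** The protocol's best estimate is 160 eligible infants a year, or 800 over five years. A consent rate below 300/800 = 37.5% then leaves fewer than 300 randomized. At the lower figure of 120 a year, which the protocol extrapolates from its observational study, the anticipated 50% consent gives 120 × 5 × 0.50 = 300, with no margin. The values 270 and 240 are illustrations, not forecasts.

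**The case against.** **The mechanism is assumed.** The package was not run, and the documents do not describe how the call treats a final size below the planned maximum. If the software takes the last look as fraction 1, the shortfall disappears. That stands as a caveat on the size. It does not remove the gap, because the critical value of the primary test should not depend on an unstated software convention.

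**The plan guards against under-recruitment.** The protocol provides for adding sites and expects a longer enrollment period if consent is below 50%. This lowers the chance of a short trial, but the five-year limit remains.

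**The error is in the safe direction.** This is correct. The relative risk estimate, the unadjusted 95% intervals and the Bayesian posteriors do not use this boundary either.

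**Stronger readings to avoid.**

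- A reader might infer that missing outcomes alone trigger the problem. With 300 randomized, 50% mortality and 90% follow-up of survivors, 150 + 135 = 285 would be assessed, and a count of 285 would give 2.086 instead of 2.004. But the SAP defines the looks and the final analysis by randomized infants. On that count a missed visit leaves the last entry at 300 and the full 5% is spent. The 285 case arises only if `vec.L` counts assessed infants, which the SAP does not say. The protocol's own projection is 320 enrolled and 304 with an outcome.
- A reader might also infer that any final z between 2.1 and 2.3 would be wrongly declared non-significant. That depends on N. At 250 the derived value is 2.283, so 2.3 rejects; at 270 the affected range is 1.993 to 2.165.

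**Conclusion.** The point holds in a limited form. The update call fixes 300 as the planned maximum, the final primary test reuses that call, and the protocol allows the trial to end with fewer than 300 infants. On the reading that alpha is spent at n/300, the final test would then run below its nominal 5%. The effect is nil at 300 and negligible at 297. It costs about 5 points of power at 270 (77.1 − 72.3 = 4.8) and about 11 at 240 (72.5 − 61.1 = 11.4).

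The conclusion rests on three assumptions: spending at n/300 at the last look, interim looks at 75, 150 and 225, and the design event rates. Type I error is not inflated and no false positive can result. The gap should be closed because it concerns the primary test, but it does not threaten the trial's validity.

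**What to change.** Keep 300 as the planned maximum for the interim looks. Add to both SAP sections (Interim Efficiency Assessment and Primary Analysis of Randomized Cohort Data):

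> If the trial ends below 300 for a reason unrelated to the interim treatment effect (such as the five-year enrollment limit), the spending fraction at the final analysis is set to 1. The final boundary is solved to spend all of the remaining two-sided 5% alpha, given the boundaries already used and the actual sample sizes.

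State also that `vec.L` counts randomized infants who have reached 22 months, as the SAP already defines the looks.

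The limit on the reason for ending is needed. The protocol also allows the trial to stop for a large mortality difference, and death is part of the primary outcome. The full-spend rule must not apply when the trial ends early because of a treatment difference, including one in mortality, since the 5% guarantee would no longer follow.

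The cost is a short SAP addition and one changed line of code, to be tested in the software that will be used. No extra infants or data are needed, and overall type I error stays at 5% under the stated condition. If 300 is reached, nothing changes.
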